2. STUDY OBJECTIVES AND ENDPOINTS

2.1 Study Objectives

2.1.1 Primary Objective

The primary objective of the study is to evaluate the long-term safety and tolerability of SBC102 in patients with liver dysfunction due to Lysosomal acid lipase (LAL) Deficiency.

2.1.2 Secondary Objectives

The secondary objectives are:

- To evaluate the long-term efficacy of SBC-102 in patients with liver dysfunction due to LAL Deficiency.
- To characterize repeat-dose pharmacokinetics (PK) of SBC-102 delivered by intravenous (IV) infusion.
- To determine the effect of SBC-102 on pharmacodynamic (PD) biomarkers.

2.1.3 Exploratory Objectives

The exploratory objectives are:

- To determine the effect of SBC-102 on Health-Related Quality of Life (HRQOL) outcome measures.
- To evaluate the acceptability of an every other week dosing regimen of SBC-102.
- To evaluate liver histology.

2.2 Study Endpoints

2.2.1 Safety Endpoints

This study is designed primarily to evaluate the safety and tolerability of long-term treatment with SBC-102, administered as weekly (qw) and biweekly (qow) IV infusions. The primary safety endpoints in this study will include:

- The incidence of:
 - Adverse events (AEs).
 - Serious adverse events (SAEs).
 - Infusion Associated reactions (IARs).
- Change/shift from baseline in:
 - Vital signs.
 - Physical examination findings.
 - Clinical laboratory tests.
 - 12-lead ECG parameters.
 - Use of concomitant medications/therapies.
- Characterization of anti-drug antibodies (ADAs) including:
 - Antibody positive rate.
 - Time to first antibody positive result.
 - Median and peak ADA titer.
 - Time to peak ADA titer.

A further characterization of ADAs, including neutralizing ADAs, may be performed as a separate pooled analysis across studies, and will be reported separately.

2.2.2 Efficacy Endpoints

The following efficacy measures will be utilized to investigate the effect of SBC-102 on hepatic dysfunction in LAL Deficiency

- Liver and spleen volumes by magnetic resonance imaging (MRI)
- Liver and spleen fat content by multi-echo gradient-echo MRI and ¹H- magnetic resonance spectroscopy (MRS) (if available)

• Histologic assessment of liver disease by biopsy in subjects who agree to the optional procedure.

2.2.3 Pharmacokinetic Endpoints

The PK endpoints are the multiple-dose (Weeks 24, 52, and 104) parameters estimated from the PK sampling times and serum SBC-102 concentrations for each dose profiled.

2.2.4 Pharmacodynamic Endpoints

The PD endpoints include observed values, change from baseline and percent change from baseline for hepatic transaminases, serum lipids and acute phase reactants at each time of assessment, overall and by dosing cohort. The percentage of subjects with abnormal transaminases at each time point will also be summarized overall and by dosing cohort.

Exploratory disease-related biomarkers, which may be identified, based on emerging information from the SBC-102 development program and scientific literature will be analyzed by changes or percent changes from baseline if the assessments are continuous.

2.2.5 Health-Related Quality of Life (HRQOL)

As there are no validated tools to assess HRQOL in LAL Deficiency, HRQOL will be assessed using tools developed for other diseases. Evidence of SBC-102 treatment benefits will be assessed by changes in scores for the following:

- Chronic Liver Disease Questionnaire (CLDQ).
- Functional Assessment of Chronic Illness Therapy-Fatigue (FACIT-Fatigue).
- The Short Form 36 Health Survey (SF-36[®]).

3. STUDY METHODS

3.1 Overall Study Design and Plan

This section of the SAP is intended to orient the reader to the study design. All information in this section is either copied or summarized from the protocol.

This Phase 2, open-label, extension study will evaluate the long-term safety, tolerability, and efficacy of SBC-102 in adult patients with liver dysfunction due to LAL Deficiency who previously received 4 doses of SBC-102 in the Phase 1/2 repeat-dose, dose escalation study (Study LAL-CL01). The study will consist of a screening period, treatment period, and follow-up period.

Subjects who successfully receive all 4 doses of SBC-102 in study LAL-CL01 and wish to continue treatment with SBC-102 in the extension study will undergo screening assessments to determine study eligibility (Note: assessments performed in study LAL-CL01 within a defined

time period may not need to be repeated at the screening visit; see Appendix A: Schedules of Assessments in the study protocol for details).

Eligible subjects will initiate treatment in the current extension study at least 4 weeks after their last dose of SBC-102 in study LAL-CL01 and continuing for up to 3 years. Each subject will initiate treatment in the extension study at the same once-weekly dose of SBC-102 that he/she received during the fourth infusion in study LAL-CL01 (i.e., 0.35 mg/kg qw, 1 mg/kg qw, or 3 mg/kg qw). After the 4th infusion under this protocol, all subjects will move to an every other week (qow) dosing regimen of 1 or 3 mg/kg.

Subsequent modifications to the dose and dosing frequency will be undertaken for individual subjects as outlined below based on observed safety and tolerability and/or clinical response to treatment. After a minimum of 12 weeks of treatment in study LAL-CL04, a subject may be considered for a dose escalation, either from 1 mg kg-1 qow to 3 mg kg-1 qow or from 3 mg kg-1 qow to 3 mg kg-1 qw, if the subject exhibits an inadequate clinical response (see below). Prior to considering a dose increase, the subject should be evaluated for other potential causes of any clinical manifestations that are thought to reflect a suboptimal response. Other causes could include:

- Missed study infusions.
- Development of a new intercurrent illness, with the potential to confound the interpretation of biochemical efficacy measures, e.g.,
 - Development of viral or autoimmune hepatitis or other alternative etiology of liver disease.
 - Initiation of a potentially hepatotoxic concomitant medication in a subject with elevated ALT.
 - Initiation or modification of concomitant medication known to impact serum lipid levels.

Inadequate clinical response is defined as:

- Clinically important manifestations of LAL Deficiency on either clinical examination, laboratory assessment, liver biopsy or imaging which have either: a) not improved from baseline,
 - b) improved and plateaued but have not normalized, or (Note: the definition of a plateauing of effect requires consideration of a minimum of 3 assessments.)
 - c) failed to normalize within 12 months of initiation of treatment.

Manifestations include but are not restricted to the following: elevated hepatic transaminases, abnormal liver function or coagulation tests, dyslipidemia, hepatomegaly, splenomegaly, significant histological abnormalities of the liver, or lymphadenopathy.

All such decisions will be made jointly by the Investigator and Sponsor.

- At Week 6 (and after at least 4 infusions), subjects receiving a starting dose of 0.35 mg/kg qw or 1 mg/kg qw will have their dose changed to 1 mg/kg qow. Similarly, subjects who were receiving a starting dose of 3 mg/kg qw for the first 4 infusions will transition to the 3 mg/kg qow regimen.
- After Week 12, subjects receiving a dose of 1 mg/kg qow may be considered for a dose increase to 3 mg/kg qow based on observed safety and tolerability and/or clinical response to treatment. Refer to Section 6.1 of the protocol for additional details.
- After Week 12, subjects receiving 3 mg/kg qow may be considered for a dose adjustment to 3 mg/kg qw based on observed safety and tolerability and/or clinical response to treatment. Refer to Section 6.1 of the protocol for additional details.
- In the event of poor tolerability at any time during the extension study, the dose may be reduced at the discretion of the Investigator. If a subject cannot tolerate the lowest starting dose (0.35 mg/kg qw) despite measures taken to manage any IARs, he/she will be discontinued from treatment.

Safety, tolerability, and efficacy assessments will be conducted at regular intervals throughout the extension study according to Appendix A: Schedules of Assessments in the study protocol. In addition, blood samples will be obtained at selected time points for analysis of SBC-102 PK and biomarkers of SBC-102 PD activity. Blood and urine samples will also be collected for an exploratory analysis of potential disease-related biomarkers in these subjects, and HRQOL measures will be assessed through subject questionnaires.

A follow-up visit will be conducted for all subjects at 30 (+7) days after the last dose of SBC102.

Figure 1: LAL-CL04 Study Flow Diagram

*After Week 12, a dose adjustment from 1 mg·kg⁻¹ qow to 3 mg·kg⁻¹ qow, or from 3 mg·kg⁻¹ qow to 3 mg·kg⁻¹ qw, may be considered based on safety and tolerability and/or clinical response to treatment. A dose reduction is permitted at any time in the event of poor tolerability.

3.2 Selection of Study Population

The target population for this study is male and female subjects (\geq 18 years of age) with liver dysfunction due to LAL Deficiency who received treatment with SBC-102 in study LAL-CL01.

3.2.1 Inclusion Criteria

A subject must meet all of the following inclusion criteria to be eligible for this study:

- 1. Subject understands the full nature and purpose of the study, including possible risks and side effects, and is willing and able to comply with all study procedures and provide informed consent.
- 2. Subject received all 4 scheduled doses of SBC-102 in study LAL-CL01 with no lifethreatening or unmanageable study drug toxicity.
- 3. Female subjects have a negative serum pregnancy test at screening, and are not breastfeeding.
- 4. Female subjects of childbearing potential are willing and able to use a highly effective and approved contraceptive method(s) from the date of informed consent until 30 days after last dose of IMP. A highly effective method of contraception is defined as fulfilling at least one of the following: a) Strict abstinence; b) Bilateral tubal ligation;

- c) Combined oral contraceptives (estrogens and progesterone), inserted, applied, implanted or injectable contraceptives on a stable dose for at least 1 month prior to the screening visit;
- d) Hormonal intra-uterine device (IUD) inserted at least 1 month prior to the screening visit;
- e) Vasectomized partner for at least 3 months prior to the screening visit;
- f) Condom with spermicide.

Women may be considered of non-childbearing potential if they are surgically sterile (i.e., total hysterectomy or bilateral salpingo-oophorectomy) or post-menopausal (defined as a complete cessation of menstruation for at least one year after the age of 45 years).

3.2.2 Exclusion Criteria

A subject who meets any of the following exclusion criteria will be ineligible for this study:

- 1. Clinically significant concurrent disease, serious inter-current illness, concomitant medications, or other extenuating circumstances that, in the opinion of the Investigator, would either interfere with study participation or the interpretation of the effects of SBC-102.
- 2. Clinically significant abnormal values on laboratory screening tests, other than liver function or lipid panel tests. Subjects with an abnormal laboratory value that is of borderline significance may be allowed to undergo repeat testing once within a 30-day period.

3.3 Treatment Masking (Blinding)

This is an open-label study and no study treatments are blinded or masked.

4. ANALYSIS AND REPORTING

4.1 Analysis of Available Data for Regulatory Filing

A CSR of available data may be produced to support regulatory filing(s). Such report of available data would likely include listings, summary tables, and graphs of safety, efficacy, PK and PD data available by a designated cutoff date prior to the regulatory filing(s). Select descriptive p-values to guide clinical judgment and interpretation of the data would be presented without adjustment for multiplicity.

4.2 Safety Data Summaries

The Safety Committee (SC) will perform periodic reviews of aggregate safety data from study LAL-CL04 on at least a biannual basis (i.e., every 6 months) from the date of enrollment of the first subject until completion of dosing for all subjects in the study. Ad-hoc reviews of safety data will also be performed by the SC on an as needed basis in the event of emerging safety signals of clinical concern in one or more subjects, including potential safety risks that meet the

pre-defined stopping rules for study treatment (see Section 7.6 of the protocol). Following each periodic and ad-hoc review of safety data, the SC will indicate whether dosing of SBC-102 may continue (or be resumed) for all subjects or a subset of subjects in the study.

4.3 Final Analysis

All final, planned analyses identified in the protocol and in this SAP will be performed after the last subject has completed the final follow-up visit and all relevant study data have been processed and integrated into the analysis database.

Any changes from the planned study analysis as described in the protocol are listed in Section 14 of this SAP. Any post hoc, exploratory analysis completed to support planned study analysis, which were not identified in this SAP, will be described in the CSR. Any results from these unplanned analyses (post hoc) will also be clearly identified in the text of the CSR.

4.4 Data Reporting by Cohort

For this study, results will be reported by cohort and overall. A subject's dose cohort will be defined by the dose of longest duration, i.e., by the subject's every-other-week dose.

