6.1.1 Dose Escalation

After a minimum of 12 weeks of treatment in study LAL-CL04, a subject may be considered for a dose escalation, either from 1 mg/kg qow to 3 mg/kg qow or from 3 mg/kg qow to 3 mg/kg qw, if the subject exhibits an inadequate clinical response (see below). Prior to considering a dose increase, the subject should be evaluated for other potential causes of any clinical manifestations that are thought to reflect a suboptimal response. Other causes could include:

- missed study infusions,
- development of a new intercurrent illness, with the potential to confound the interpretation of biochemical efficacy measures, e.g.,
 - development of viral or autoimmune hepatitis or other alternative etiology of liver disease,
 - initiation of a potentially hepatotoxic concomitant medication in a subject with elevated ALT
 - initiation or modification of concomitant medication known to impact serum lipid levels.

Inadequate clinical response is defined as:

- Clinically important manifestations of LAL Deficiency on either clinical examination, laboratory assessment, liver biopsy or imaging which have either
 - a. not improved from baseline,
 - b. improved and plateaued but have not normalized,
 (Note: The definition of a plateauing of effect requires consideration of a minimum of 3 assessments.)
 - c. failed to normalize within 12 months of initiation of treatment.

Manifestations include but are not restricted to the following: elevated hepatic transaminases, abnormal liver function or coagulation tests, dyslipidemia, hepatomegaly, splenomegaly, significant histological abnormalities of the liver, or lymphadenopathy.

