6.1.2 Dose Reduction

Subjects who do not tolerate their current dose level may receive a dose reduction to the next lowest dose level, i.e., 1 mg/kg qow or 0.35 mg/kg qow, at the discretion of the Investigator in consultation with the Sponsor and, where appropriate, the SC.

If a subject cannot tolerate a dose of 0.35 mg/kg qow, despite measures taken to manage any IARs, the subject will be discontinued from the study.

NOTE: Any subject who undergoes a dose modification, as described above, will have additional laboratory monitoring schedule of selected analytes, as detailed in Section 5.1.10.

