5. STATISTICAL ANALYSIS

5.1 General Statistical Methodology

All data will be provided in listings sorted by cohort and subject study number, and, if applicable, date of assessment. Dates will be provided in the ISO8601 yyyy-mm-dd format (eg, 2013-01-01). Where a time component is included (24 hour clock with hour and minute) the format will be yyyy-mm-dd:hh:mm (eg, 2012-01-01:16:32). Included in all listings will be the dosing cohort for each subject. Select listings will also include the dosing regimen that each subject was on at the onset of the event.

Tabulations will be prepared using the following descriptive statistics:

- Continuous, quantitative variable summaries will include the number of subjects with non-missing values (n), mean, standard deviation (SD), minimum, median, and maximum. In addition, the percent coefficient of variation (CV%) will be provided for PK parameters.
- Categorical, qualitative variable summaries will include the frequency and percentage of subjects who are in the particular category. In general, the denominator for the percentage calculation will be based upon the total number of subjects in the analysis set for the cohort. Shift tables comparing data observed at baseline to that observed after the initiation of dosing will be prepared as noted for specific endpoints.

95% two-sided confidence intervals (CI) may be calculated around the estimates based on the exact binomial distribution for categorical endpoints and the t-distribution for continuous endpoints. Confidence intervals will be based on a 2-sided alpha of 0.05 and are intended to guide clinical judgment and interpretation of the data. Effect of anti-drug antibodies may be examined for efficacy, safety, and PK endpoints. Additional exploratory analyses may be conducted in other subgroups of interest.

Baseline values are defined as the last measurement prior to the first infusion of SBC-102 in study LAL-CL04.

For select continuous efficacy, safety, and HRQOL endpoints that are computed as changes from baseline, change from the CL04 Baseline will be presented. All tabulations will present data overall and by dosing cohort.

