11.2 Adverse Events

An AE is any untoward medical occurrence in a subject, which does not necessarily have to have a causal relationship with the administration of a pharmaceutical product. An AE can therefore be any unfavorable and unintended sign, symptom or disease temporally associated with the use of the medicinal product, whether or not considered related to the medicinal product. Pre-existing conditions that worsen in severity during the course of the study are to be reported as AEs.

Severity of AEs will be graded on a 5-point scale (mild, moderate, severe, life-threatening and death) according to National Cancer Institute (NCI) Common Terminology Criteria for Adverse Events (CTCAE), version 4.03. All AEs will be coded using the Medical Dictionary for Regulatory Activities (MedDRA[®]), version 13.1 or higher.

In AEsummaries, subjects will only count in one column.

For counting events, if a subject experiences the same AE multiple times, each occurrence of this event will be counted toward the frequency of events; but for counting subjects, each subject will be counted only once within each PT and each SOC. If a subject experiences more than one AE within a PT or SOC, only the AE with the strongest relationship or the greatest severity, as appropriate, will be included in the summaries of relationship and severity, respectively.

A data listing of all AEs reported in the study will be presented.

Additionally a data listing of deaths and AEs leading to study discontinuation will be provided.

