11.2.1 Serious Adverse Events

Summaries of the numbers of SAEs and incidence rates (frequencies and percentages of subjects), by PT within SOC, overall and by dosing cohort, will be prepared for the Safety Analysis Set.

A data listing of SAEs will be provided.

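### By-cohort tables give each subject one label, the dose held longest, so after a dose change some adverse events and responses are tabulated under a dose the subject was not receiving

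*SAP*

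**What the plan says.** SAP 4.4 sets the rule: a subject's "dose cohort will be defined by the dose of longest duration", which the same sentence equates with the dose given every other week. SAP 14 item 4 repeats it as a declared change from the protocol and gives no reason. SAP 5.1 makes it general: "All tabulations will present data overall and by dosing cohort". For adverse events, SAP 11.2 adds: "In AEsummaries, subjects will only count in one column". SAP 11.2.1 says that SAE summaries "by PT within SOC, overall and by dosing cohort, will be prepared for the Safety Analysis Set".

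The protocol planned something different. Section 8.1 tabulates by dosing regimen, meaning dose and frequency together, and section 8.7 intends to explore the effect of regimen on safety where appropriate.

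Doses may change for cause. Protocol 6.1.1 allows escalation after at least 12 weeks "if the subject exhibits an inadequate clinical response". Protocol 3.1 words the grounds more broadly, as safety and tolerability and/or response. Protocol 6.1.2 covers the other direction: "Subjects who do not tolerate their current dose level may receive a dose reduction to the next lowest dose level".

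The SAP departs from the cohort label in three places. Select listings show "the dosing regimen that each subject was on at the onset of the event" (SAP 5.1), exposure is summarized by dose (SAP 11.1), and PK concentrations are summarized by dose at the infusion (SAP 8.1.4).

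**The concern.** The label is not fixed at the start of treatment. It depends on how long each dose lasted, and so on tolerability and response during the study. If an AE leads to an early dose reduction, the reduced dose can become the longest, and the AE is then tabulated under a dose that was not being given when it occurred. If a subject is escalated early from 1 to 3 mg/kg every other week, the response on 1 mg/kg is summarized under 3 mg/kg.

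Safety is the primary objective, and with so few subjects one moved event can empty a column. AEs by cohort also will not line up with exposure, which is by dose.

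The second half of the SAP 4.4 sentence does not settle the matter. It equates the longest dose with the every-other-week dose, but a subject may have two such doses. A subject may also spend longest on 3 mg/kg weekly, which is not an every-other-week regimen at all.

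**Working it through.** The plan states no figure for this point, so the check is time-on-dose arithmetic.

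**Inputs**
- Follow-up T: 260 weeks (5 years; Protocol 3.2.3 and the assessment schedule) or 156 weeks (3 years; SAP 3.1). The documents differ, so both are shown.
- Clock start s: Week 6 if only every-other-week time counts (Protocol 6.1), or 0 if the same mg/kg dose was given from the start.
- One dose change, at week w (assumption).

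**When the later dose becomes the label.** Time on the first dose is w − s and on the later dose T − w. The later dose is longest when T − w > w − s, that is w < (T + s)/2.
- T = 260: (260 + 6)/2 = 133, or 260/2 = 130.
- T = 156: (156 + 6)/2 = 81, or 156/2 = 78.

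**Share of every-other-week time filed under the wrong dose (s = 6).** This is the shorter stretch over the total, min(w − 6, T − w)/(T − 6), so it cannot exceed one half.

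| Change at week | T = 260: label; share | T = 156: label; share |
|---|---|---|
| 24 | later; 18/254 = 7% | later; 18/150 = 12% |
| 52 | later; 46/254 = 18% | later; 46/150 = 31% |
| 104 | later; 98/254 = 39% | first; 52/150 = 35% |
| 140 | first; 120/254 = 47% | first; 16/150 = 11% |

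A change at Week 104 gives a different label under the two stated durations.

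**Interim against final.** For a change at Week 60 (s = 6), the first dose has lasted 60 − 6 = 54 weeks. The later dose overtakes it at 60 + 54 = Week 114. A data cut before then labels the subject by the first dose and a later cut by the second, so the same AEs change column. SAP 4.1 allows such an interim report.

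**Effect on an AE table (illustration).** Assume 9 subjects, with one AE on 3 mg/kg followed by an early reduction to 1 mg/kg. The splits are assumed because the documents give none.

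| Split, 1 / 3 mg/kg | By dose at onset: 3 mg/kg column | SAP label: 3 mg/kg column | SAP label: 1 mg/kg column |
|---|---|---|---|
| 3 / 6 | 1/6 = 16.7% | 0/5 | 1/4 = 25.0% |
| 4 / 5 | 1/5 = 20.0% | 0/4 | 1/5 = 20.0% |
| 5 / 4 | 1/4 = 25.0% | 0/3 | 1/6 = 16.7% |
| 6 / 3 | 1/3 = 33.3% | 0/2 | 1/7 = 14.3% |

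By dose at onset the 1 mg/kg column has no event. Under the SAP label the event changes column in every split.

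**The case against.** The best defence is that this matters little. The analysis is descriptive, SAP 12 plans no formal test between cohorts, and SAP 14 discloses the rule. Protocol 8.7.1 puts the regimen before each event in the by-subject listings, so with at most 9 subjects a careful reader could trace any event. All of this stands, and it limits the severity. It does not make the tables right: they are what a reader of the report sees first, and SAP 7 and 9 attach 95% confidence intervals to the by-cohort efficacy and PD results.

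A second defence is that the every-other-week gloss fixes the label, since Protocol 3.1 determines the first such dose from the starting dose. That works for subjects with only one every-other-week dose. It fails for those with two, who are the subjects at issue. For a move from 3 mg/kg every other week to weekly, the mg/kg column is the same on either reading, but the change of frequency is hidden.

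A reader might infer more than the documents support:
- **That the bias always runs one way, clearing events from the higher dose and keeping good responders in the lower.** It does not. After a late reduction the causal AE stays under the higher dose, and later lower-dose events are added to it.
- **That escalation occurs only for inadequate response.** Protocol 3.1 is broader than 6.1.1.
- **That events on 0.35 mg/kg can never appear under that dose.** A subject who stops before Week 6, or is later reduced to 0.35 mg/kg and stays there longest, could carry that label.
- **That a spurious efficacy gap of a definite size follows.** This would need an assumed response distribution, cohort split and escalation threshold. The documents give none of these, and the criteria in 6.1.1 are not a percent-change cutoff.

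**Conclusion.** The concern holds as a should-fix. For any subject whose mg/kg dose changes, the by-cohort tables report part of the data under a dose not being given at the time, and which part depends on post-baseline tolerability or response. With one change, that part is the shorter stretch, at most half of the follow-up. The direction turns at about Week 130–133 under the protocol's duration and Week 78–81 under the SAP's.

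How much this matters in practice depends on how many subjects change dose and when, which the documents do not say. The AE illustration rests on assumed splits and a single event. The damage is confined to descriptive by-cohort columns. Overall columns, exposure by dose and PK concentrations are not affected, although SAP 8.2 still summarizes PK parameters by cohort.

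**What to change.** Amend SAP 4.4, 11.2 and 14 before database lock.

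1. Tabulate AEs, SAEs and infusion-associated reactions by the regimen in force at onset. This restores the grouping in Protocol 8.1 and uses information already captured for listings. Let a subject count in more than one regimen column and once in Overall, and show subject-time or number of infusions per regimen beside the counts.
2. Group by-visit efficacy, PD and quality-of-life tables by the every-other-week regimen that the protocol assigns for Week 6, and flag visits after a dose change. That regimen follows from the starting dose, so it is known before the first extension infusion and cannot shift between reports. Starting dose itself is a poorer grouping, because it separates the 0.35 and 1 mg/kg starters, who share one assigned regimen from Week 6.
3. Give the reason for the final choice of grouping in SAP 14.

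The 3-year and 5-year durations should be reconciled in any case, but these groupings no longer depend on them.

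The cost is SAP text and table shells, with no new data and no change to patient care. One small downside is that AE columns will no longer sum to the number of subjects, which a footnote can explain.
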